3. STUDY DESIGN

3.1 Study Description and Duration

This prospective, open-label, single-center, randomized, fellow-eye, investigator-sponsored clinical study seeks to investigate the safety and efficacy of the dexamethasone insert in the treatment of allergic conjunctivitis and DED signs and symptoms in patients with Keratoconus using RGP contact lenses when compared to topical standard of care loteprednol etabonate ophthalmic gel 0.38%. After screening a given patient for inclusion and exclusion criteria, and gaining informed consent, one eye will be randomized to receive the dexamethasone insert as determined by a coin flip at the screening visit. The remaining eye will be prescribed a loteprednol etabonate ophthalmic gel 0.38% following a 4,3,2,1 weekly taper. Per enrolled eye, the study period will last for approximately 90 days, consisting of five visits. At Screening/ Baseline, Day 0, Day 7, Day 30 and Day 90, primary and secondary endpoints will be assessed alongside standard-of-care procedures. Adjusting for enrollment period, the study will last a total of approximately 3 months. An abstract with preliminary results will be submitted by May 2020 for the AAOpt conference.

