1.2.1 Rationale for Study Design

This prospective study will use a fellow-eye design for 20 participants (40 eyes) with bilateral keratoconus, wearing RGP contact lenses in both eyes, who have been diagnosed with bilateral allergic conjunctivitis and underlying dry eye disease. Per participant, one eye will be randomized to receive the intracanalicular dexamethasone insert at the baseline visit (study eye), while the other eye will be assigned to receive the standard of care topical lotemax etabonate ophthalmic gel 0.38% (control eye). Thus, for every eye in the study group, there will be a paired eye with similar baseline characteristics in the control group sourced from the same participant. The fellow-eye design allows for greater control of potential confounders tied to participants' systemic and ocular health.

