2. STUDY OBJECTIVES

2.1 Primary Objective

To determine the effect of dexamethasone intracanalicular insert through Day 90 as measured by:

- Mean change in itching score from Baseline measured at all visits (Visits 1-5)
 - Graded on a scale of 0-4 and determined by asking the patient
- Mean change in palpebral conjunctivitis papillae score from Baseline measured at all visits (Visits 1-5)
 - Graded using the Papillae Efron Scale as graded by the physician
- Mean change in conjunctival injection score from Baseline measured at all visits (Visits 1-5)
 - Graded on a scale of 0-4 as graded by the physician
- Mean change in corneal staining score from Baseline measured at all visits (Visits 1-5)
 - Graded using the NEI Fluorescein Staining Scale as graded by the physician

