4.1.1 Inclusion Criteria

A patient's study eye must meet the following criteria to be eligible for inclusion in the study:

- 18 years of age or older
- Bilateral Keratoconus
- Bilateral RGP contact lenses
- Bilateral allergic conjunctivitis as determined by the Papillae Efron Scale score of at least 1 and symptoms of itching
- Bilateral underlying dry eye disease as determined by the NEI Fluorescein Staining Scale score of at least 1 and a TBUT of less than 10 and must correlate with dryness on OSDI

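### The insert eye is chosen by a coin flip made when both eyes' scores are known, with no concealment, binding rule or record specified

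*Combined protocol and SAP*

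**What the plan says.** Section 3.1 gives the only description of the allocation mechanism: "one eye will be randomized to receive the dexamethasone insert as determined by a coin flip at the screening visit". It places the flip after other steps: "After screening a given patient for inclusion and exclusion criteria, and gaining informed consent". Section 1.2.1 also ties the randomisation to the baseline visit, which Table 1 labels Visit 1, and adds nothing on method.

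Eligibility under Section 4.1.1 depends on findings in both eyes: "Bilateral allergic conjunctivitis as determined by the Papillae Efron Scale score of at least 1 and symptoms of itching", and "Bilateral underlying dry eye disease as determined by the NEI Fluorescein Staining Scale score of at least 1 and a TBUT of less than 10".

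Section 3.1 describes the design as "This prospective, open-label, single-center, randomized, fellow-eye, investigator-sponsored clinical study". The three sign endpoints in Section 2.1 are physician-graded; for conjunctival injection the text is "Graded on a scale of 0-4 as graded by the physician". All four primary endpoints are mean changes from baseline. The document has no statistical analysis section, so no baseline adjustment is described.

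Neither Table 1 nor the Visit 1 list in Section 5.2.1 has a randomisation step. The accountability records in Section 4.2.3 cover the inserts used, returned or disposed of. They do not cover the flip or the eye it selected. Table 1 allows Visit 1 to fall 1 to 30 days before insertion at Visit 2.

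**The concern.** Nothing says who flips the coin, which face stands for which eye, whether the first result is final, or where it is written down. The person who flips may know which eye is worse. Section 1.1 describes keratoconus as asymmetric, so there may well be a worse eye to prefer.

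A repeat need not be made in bad faith. The exclusion for an obstructed nasolacrimal duct in Section 4.1.2 is worded for the study eye(s), and the synopsis defines the study eye as the one that receives the insert. If the coin selects an obstructed eye, the protocol does not say whether the patient is excluded or the coin is flipped again.

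At stake is the between-eye comparison. An eye chosen because it scored worse at baseline will, on average, score closer to its fellow at the next visit with no treatment effect at all. With change from baseline as the endpoint, that movement is credited to whichever treatment the worse eye received.

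**Working it through.** The plan states no SD, reliability, alpha, power or sample-size calculation, so it has no figure to reproduce. What follows sizes what the procedure would permit.

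**Inputs.** From the documents: 20 patients, one insert eye and one control eye each, endpoint change from baseline. Assumed: SD of the between-eye baseline difference = 1 grade; reliability r of that difference = 0.6 to 0.8; normal data; a share f of patients in whom the worse eye is always sent to the same treatment, with honest flips in the rest.

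**Baseline difference caused by steering.** The mean absolute value of a normal difference is √(2/π) × SD = 0.798 × SD. The eyes given the favoured treatment therefore start worse by m = f × 0.798 × SD.

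**Bias in the between-eye change.** A fraction (1 − r) of m disappears on re-measurement, so bias = f × 0.798 × SD × (1 − r). For f = 0.25 and r = 0.8: 0.25 × 0.798 × 1 × 0.2 = 0.04.

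**Visibility at baseline.** With SD = 1, the standard error of the mean baseline difference is √(1 − m²)/√20.

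| Share steered | m (SE) | Bias, r = 0.8 | Bias, r = 0.7 | Bias, r = 0.6 |
|---|---|---|---|---|
| 25% | 0.20 (0.22) | 0.04 | 0.06 | 0.08 |
| 50% | 0.40 (0.21) | 0.08 | 0.12 | 0.16 |
| 100% | 0.80 (0.13) | 0.16 | 0.24 | 0.32 |

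The bias scales with the SD. At 0.5 grade the 25% row becomes 0.02 to 0.04 and the 50% row 0.04 to 0.08. Corneal staining is a total over several areas (Appendix IV), so for that endpoint read the table in units of the between-eye SD.

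**What one repeat does.** Re-flipping once whenever the unwanted eye comes up gives P(preferred eye) = 0.5 + 0.5 × 0.5 = 0.75. Since P = 0.5 + f/2, this is the 50% row.

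**False-positive rate.** This was simulated with 20 pairs, no treatment effect, a paired t-test on the between-eye difference in change, two-sided 5% (test and alpha assumed) and 50,000 runs per setting. With P = 0.75 the rate is 6.7%, 10.1% and 14.2% at baseline-to-follow-up correlations of 0.9, 0.7 and 0.5. With P = 0.60 (f = 0.20) and a correlation of 0.7 it is 5.8%. With P = 0.50 it stays at 4.9% to 5.2%.

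**The case against.** The strongest reply is that a fair coin is a valid randomiser. It is unpredictable, it adds no bias, and the fellow-eye design makes each patient his or her own control. All of that is true of an honest flip. It does not answer the point that the plan has nothing to make the first result stick or to show later that it did.

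The size also depends on assumptions. Preferences that differ between patients would partly cancel, and adjusting for the between-eye baseline difference would remove much of the bias. Both points stand, although no such adjustment is described.

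Several stronger readings are tempting but not supported:

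- A reader might infer that the flip goes unrecorded. The protocol is silent; the most that can be said is that no record is specified.
- A reader might infer that an audit could never find steering. Both eyes are scored at Visit 1, so steering every patient would be plain (0.80 against an SE of 0.13). At 50% it is borderline, and at 25% it would usually be missed.
- A reader might fault the flip because unmasked staff have already scored both eyes. No allocation exists at that moment, so there is nothing to be masked to, and scoring before allocation is the right order. The exposure is that those scores are known to someone who may control the flip.
- A reader might call randomisation the study's only protection. Section 1.2.1 also relies on within-patient pairing to control confounding.
- A reader might object to chance imbalance between right and left eyes. Twenty fair flips do give 14:6 or worse in 11.5% of trials and 15:5 or worse in 4.1%, but the arms stay at 20 eyes each, a fair coin adds no bias, and the documents describe no systematic right-left difference.

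**Conclusion.** The concern holds as a weakness in how allocation is secured, not as a finding that allocation was biased. The stated method can be repeated or overridden by someone who knows which eye is worse, and light to moderate steering could not be verified afterwards.

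Under the assumptions above, the bias is modest for a single endpoint, at most 0.16 grade with half the patients steered. One re-flip per unwanted result is still enough to double the nominal 5% error rate at a correlation of 0.7. These figures require consistent steering in one direction, Visit 1 scores as the baseline, and analysis of unadjusted changes.

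**What to change.** In Section 3.1, replace the coin flip with a computer-generated list of right/left assignments, prepared by an existing staff member who does not examine or grade patients. Use an unblocked list, or a single permuted block of 20. Small blocks should be avoided, because in a single-centre open-label study they make some assignments guessable; with one block of 20 that risk is confined to the last few.

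Hold the list in sequentially numbered opaque sealed envelopes or in the electronic data system. Open each assignment only after consent, eligibility and the pre-treatment scores of both eyes are recorded. Preferably these are the Day 0 pre-insertion scores, since a Visit 1 allocation can be known for up to 30 days before they are graded. State that the assignment is binding, and how a patient is handled if the assigned eye proves unsuitable. Log the eye, date, time and operator on the case report form, add the step to Table 1, and align the timing in Section 1.2.1.

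The cost is about an hour of preparation and one protocol sentence, plus these small conforming edits. No visits are added. It has to be done before enrolment, because an undocumented flip cannot be reconstructed.

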4. SELECTION, WITHDRAWAL, AND REPLACEMENT OF PATIENTS

4.1 Study Population

The study aims to enroll 20 patients with keratoconus, who have been diagnosed with allergic conjunctivitis and underlying dry eye disease.

4.1.1 Inclusion Criteria

A patient's study eye must meet the following criteria to be eligible for inclusion in the study:

- 18 years of age or older
- Bilateral Keratoconus
- Bilateral RGP contact lenses
- Bilateral allergic conjunctivitis as determined by the Papillae Efron Scale score of at least 1 and symptoms of itching
- Bilateral underlying dry eye disease as determined by the NEI Fluorescein Staining Scale score of at least 1 and a TBUT of less than 10 and must correlate with dryness on OSDI

4.1.2 Exclusion Criteria

A patient who meets any of the following criteria will be excluded from the study:

- Patients under the age of 18.
- Pregnancy (must be ruled out in women of child-bearing age with pregnancy test)
- Active infectious systemic disease
- Active infectious ocular or extraocular disease
- Obstructed nasolacrimal duct in the study eye(s)

- Hypersensitivity to dexamethasone
 - Patients being treated with immunomodulating agents in the study eye(s)
 - Patients being treated with immunosuppressants and/or oral steroids
- Patients with severe disease that warrants critical attention, deemed unsafe for the study by the investigator

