Investigator-Initiated Trial Study Protocol

Safety and Efficacy of an Intracanalicular Dexamethasone Insert compared to Topical Loteprednol Etabonate Ophthalmic gel 0.38% in Patients with Keratoconus (KC) wearing Rigid Gas Permeable (RGP) Contact Lenses who have been diagnosed with Allergic Conjunctivitis and underlying Dry Eye Disease (DED)

The [name] Study

Compound: DEXTENZA (dexamethasone ophthalmic insert) 0.4 mg, for intracanalicular use

Study Name: The [name] STUDY

Clinical Phase: Open-label, Prospective, Interventional

Date of Issue: February 20, 2020

Primary Investigator: [name], OD
[contact]

Research Coordinator: [name]
Senior Research Coordinator

Site Name & Location: Cornea Center for Clinical Excellence
Illinois College of Optometry
Illinois Eye Institute
[contact]

CLINICAL STUDY PROTOCOL SYNOPSIS

TITLE	Safety and Efficacy of an Intracanalicular Dexamethasone Insert compared to Topical Loteprednol Etabonate Ophthalmic gel 0.38% in Patients with Keratoconus (KC) wearing Rigid Gas Permeable (RGP) Contact Lenses who have been diagnosed with Allergic Conjunctivitis and underlying Dry Eye Disease (DED)- The [name] Study
SITE LOCATION(S)	Cornea Center for Clinical Excellence Illinois College of Optometry Illinois Eye Institute [contact]
PRINCIPAL INVESTIGATOR	[name], OD [contact]
OBJECTIVE(S)	To determine if physician administered intracanalicular dexamethasone insert improve the signs and symptoms of ocular allergy and dry eye disease in KC patients compared to topical loteprednol etabonate ophthalmic gel 0.38%.
STUDY DESIGN	Prospective Open-label Interventional Study
STUDY DURATION	4 months after IRB approval
ESTIMATED STUDY COMPLETION DATE	3 months after DEXTENZA insertion
POPULATION	
Sample Size:	20 patients (40 eyes)
Target Population:	Patients with bilateral keratoconus, wearing RGP contact lenses in both eyes, who have been diagnosed with bilateral allergic conjunctivitis and underlying dry eye disease
TREATMENT(S)	
Study Drug	DEXTENZA (dexamethasone ophthalmic insert) 0.4 mg, for intracanalicular use
Dose/Route/Schedule:	Patients with Keratoconus, with Allergic Conjunctivitis and underlying Dry Eye Disease, wearing RGP contact lenses will have one eye randomized to receive the Sustained Release Dexamethasone, 0.4mg intracanalicular insert (study eye). The fellow-eye will receive topical loteprednol (control eye) on a 4,3,2,1 weekly taper schedule.
ENDPOINT(S)	

Primary:

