5.3 Rescue Criteria

Patients can be rescued at any time at the discretion of the investigator with loteprednol etabonate ophthalmic gel 0.38%. Rescue criteria includes:

- A score greater than or equal to 2+ in one or more of the following categories:
 - Itching
 - Papillae
 - Injection
 - Staining

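### The only hypersensitivity exclusion names dexamethasone, yet every participant is also assigned loteprednol, so a patient with known loteprednol hypersensitivity is eligible as written

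*Combined protocol and SAP*

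**What the plan says.** The exclusion list in Section 4.1.2 works at patient level, and any one item is enough: "A patient who meets any of the following criteria will be excluded from the study". Its only item on drug hypersensitivity reads "Hypersensitivity to dexamethasone". Its only item that invokes the investigator's judgement reads "Patients with severe disease that warrants critical attention, deemed unsafe for the study by the investigator".

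The comparator is assigned to all participants. The Synopsis states "The fellow-eye will receive topical loteprednol (control eye) on a 4,3,2,1 weekly taper schedule". Section 3.1 repeats it: "The remaining eye will be prescribed a loteprednol etabonate ophthalmic gel 0.38% following a 4,3,2,1 weekly taper". Section 1.2.1 gives the reason for pairing: "Thus, for every eye in the study group, there will be a paired eye with similar baseline characteristics in the control group". The planned size is 20 patients, 40 eyes.

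The rescue provision in Section 5.3 uses the same product: "Patients can be rescued at any time at the discretion of the investigator with loteprednol etabonate ophthalmic gel 0.38". It does not say whether the rescued eye is the insert eye, the control eye or both.

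**The concern.** In a parallel-group trial, a hypersensitivity criterion limited to the experimental drug would already leave the comparator arm uncovered. In a fellow-eye trial the gap extends to everyone, because each participant is assigned both drugs. A patient who cannot take one of them cannot follow the protocol, whichever eye the coin flip selects for the insert.

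What is at stake is participant safety and the coherence of the eligibility rule. The protocol wrote a specific criterion for one of its two drugs and none for the other. The rescue text adds to the difficulty. Itching or injection of 2+ or more is a rescue criterion in 5.3, and the named rescue product is loteprednol. The plan does not say what happens if the reaction being rescued is a reaction to that product.

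**Working it through.** No arithmetic beyond counting applies, and the plan gives no figure to reproduce. The check is whether any part of the document closes the gap.

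1. **Drugs planned per participant.** Synopsis, 1.2.1 and 3.1: one eye receives the dexamethasone insert and the other loteprednol gel 0.38%. With 20 patients this gives 20 insert eyes + 20 loteprednol eyes = 40 eyes. Planned assignment to loteprednol is therefore 20/20 = 100% of patients. This is assignment under the plan, not observed exposure.

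2. **Exclusion criteria (4.1.2).** There are nine items: age under 18; pregnancy; active systemic infection; active ocular or extraocular infection; nasolacrimal duct obstruction; dexamethasone hypersensitivity; immunomodulating agents in the study eye; immunosuppressants or oral steroids; and severe disease judged unsafe. One of the nine concerns hypersensitivity. None names loteprednol, corticosteroids as a class, or components of either product. The item on oral steroids concerns current treatment, not intolerance.

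3. **Inclusion criteria (4.1.1).** These cover age, keratoconus, lens wear, allergic conjunctivitis and dry eye disease. Drug hypersensitivity is not mentioned.

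4. **Discretionary exclusion (last item of 4.1.2).** The judgement of safety is attached to severe disease. A patient with mild or moderate disease and a known loteprednol hypersensitivity does not meet it as worded.

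5. **Other sections.** Section 4.3 allows other medications to continue and says nothing on this point. Table 1 and Section 5.2.1 collect medical history at Visit 1, before the insertion visit, so a known hypersensitivity could come to light. No rule says what follows from it.

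6. **Rescue (5.3).** The gel may be given again as rescue, with the eye unspecified. No exception is written for a patient who does not tolerate it, although rescue is at the investigator's discretion.

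**Result.** Applied literally, the criteria admit a patient known to be hypersensitive to a drug that all 20 participants are assigned.

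**The case against.** The strongest reply is that such a patient would rarely be given the gel in practice. Loteprednol is described as standard of care and is prescribed by a clinician. Medical history is taken before Day 0. Section 7.1 binds the investigator to GCP and the Declaration of Helsinki, and rescue is discretionary. All of this makes harm less likely. None of it is an eligibility criterion, however, and the protocol did not rely on such judgement for dexamethasone. The reply lowers the likely number affected but does not close the gap.

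A second reply is that the sections do not contradict each other. That is right: this is an omission, and all the passages can be followed at once. The trouble is that following them exactly leads to an outcome the authors presumably did not intend.

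A reader might go further and infer that a reaction in the control eye would raise itching and injection there, both primary endpoints, and so flatter the insert. The documents do not support that conclusion:

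- They give no rate of hypersensitivity, so no effect on a 20-patient mean can be shown.
- The argument needs a patient with a known history to be enrolled and still treated. Reactions in patients without a known history would occur under any wording of the criterion.
- Because 5.3 does not name the eye, rescue could expose insert eyes too, and a reaction there would push the other way.
- Appendix I asks the patient for a current level of itching and does not say that each eye is scored separately.

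A reader might also take 5.3 as providing loteprednol rescue for either eye. The text leaves the eye open. It neither grants nor excludes this.

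**Conclusion.** The omission is real and can be read directly from the text. Eligibility addresses hypersensitivity to one of the two drugs assigned to every participant, and no other provision covers the second. Planned assignment to the uncovered drug is 20 of 20 patients. The number who would actually be affected cannot be stated from the documents and is probably small.

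This is a safety and consistency point that should be corrected. It alters no sample size, estimate or test, and it does not establish bias in any endpoint.

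The conclusion assumes that the exclusion list is complete as printed (nothing suggests text was lost) and that the criteria are applied as written. It makes no assumption about whether hypersensitivity to dexamethasone predicts hypersensitivity to loteprednol, on which the documents are silent. Even if the two overlapped, a patient hypersensitive to loteprednol alone would still be admitted.

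**What to change.** Reconcile the hypersensitivity criterion in 4.1.2 with the treatment assignment in 3.1 (and the Synopsis and 1.2.1) and with the rescue provision in 5.3, so that eligibility is consistent with the drugs participants are assigned. The clinical wording is for the investigator and the IRB to decide. In the same revision, the investigator should state which eye the rescue provision refers to, because 5.3 leaves this open.

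The cost is about one phrase in 4.1.2, a clarification in 5.3 and the IRB approval that Section 7.4 requires before an amendment is implemented. An occasional additional screen failure is possible. How often cannot be estimated, since the documents give no frequency. No analysis or sample-size statement needs to change.

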4.2 Treatment Logistics and Accountability

4.2.1 Packaging, Labeling, and Storage

Intracanalicular dexamethasone insert must be stored in a secure area accessible only to the Investigator and their designee(s) and refrigerated and stored between 2° C and 8° C. Intracanalicular dexamethasone insert contains 0.4 mg dexamethasone and is designed to provide a sustained and tapered release of therapeutic levels of dexamethasone to the ocular surface for up to 30 days for the reduction of post-surgical inflammation and pain associated with ocular surgery. Dexamethasone is an anti-inflammatory 9-fluoro-glucocorticoid (also termed a glucocorticoid agonist) and is the active ingredient found in MAXIDEX[®] 0.1% (dexamethasone ophthalmic suspension), which contains approximately 50 µg of dexamethasone per drop.

Study inserts will be supplied by Ocular Therapeutix in a sealed foil pouch containing one intracanalicular dexamethasone insert in a foam carrier.

Study inserts will be shipped to the site via overnight shipping using cold packs to maintain a temperature of 2° to 8° C. The Investigator, or an approved representative (e.g. pharmacist), will ensure that all study drug inserts are stored in a secured area, under recommended storage conditions and in accordance with applicable regulatory requirements. The shipping box is to be opened and stored immediately at the site in a refrigerator intended for investigational products at a temperature of 2° to 8°C.

When the insert is removed from the refrigerator, it should be visually inspected. Exposure of the insert to temperatures outside these limits is not recommended. Records of actual storage conditions (i.e. temperature log) at the study site must be maintained; and must include a record of the dates, when the refrigerator was checked, the initials of person checking, and the temperature.

